8.3 Serious Adverse Events

An adverse event or adverse reaction is considered serious if, in the view of either the Investigator or Sponsor, it results in any of the following outcomes:

- Death,
- A life-threatening adverse event,
 - Note: An adverse event or adverse reaction is considered "life-threatening" if, in view of either the Investigator or Sponsor, its occurrence places the patient at immediate risk of death. It does not include an event that, had it occurred in a more severe form, might have caused death.
- Requires hospitalization or prolongation of existing hospitalizations,
 - Note: Any hospital admission with at least 1 overnight stay will be considered an inpatient hospitalization. An emergency room visit without hospital admission will not be recorded as an SAE under this criterion, nor will hospitalization for a procedure scheduled or planned before signing of informed consent. However, unexpected complications and/or prolongation of hospitalization that occur during elective surgery should be recorded as adverse events and assessed for seriousness. Admission to the hospital for social or situational reasons (ie, no place to stay, live too far away to come for hospital visits) will not be considered inpatient hospitalizations.
- A persistent or significant disability/incapacity or substantial disruption of the ability to conduct normal life functions,
- A congenital anomaly/birth defect, or
- An important medical event.
 - Note: Important medical events that may not result in death, be life-threatening, or require hospitalization may be considered an SAE when, based upon appropriate medical judgment, they may jeopardize the patient and may require medical or surgical intervention to prevent one of the outcomes listed above. Examples of such medical events include allergic bronchospasm requiring intensive treatment in an emergency room or at home, blood dyscrasias or convulsions that do not result in inpatient hospitalizations, or the development of drug dependency.

8.4 Serious Adverse Event Reporting – Procedures for Investigators

Initial Reports

All SAEs occurring from the time of informed consent until 30 days following the last administration of study drug must be reported to Worldwide Drug Safety within 24 hours of the knowledge of the occurrence (this refers to any adverse event that meets any of the aforementioned serious criteria). All SAEs that the Investigator considers related to study drug occurring after the 30-day follow-up period must be reported to the Sponsor.

To report the SAE, complete the SAE form electronically in the electronic data capture (EDC) system for the study. When the form is completed, Worldwide Drug Safety personnel will be notified electronically and will retrieve the form. If the event meets serious criteria and it is not possible to access the EDC system, contact Worldwide Drug Safety by email or phone, and fax

the completed paper SAE form (e-mail address and phone and fax numbers listed below) within 24 hours of awareness. When the EDC system becomes available, the SAE information must be entered within 24 hours.

- Safety Contact Information: Site staff will complete the paper SAE report form and e-mail it within 24 hours to the following address: [contact].
- In cases where the email system is unavailable, site staff will send the SAE by fax to: [contact] (US) and [contact] (ROW).

Follow-Up Reports

The Investigator must continue to follow the patient until the SAE has subsided or until the condition becomes chronic in nature, stabilizes (in the case of persistent impairment), or the patient dies.

Within 24 hours of receipt of follow-up information, the Investigator must update the SAE form electronically in the EDC system for the study and submit any supporting documentation (eg, patient discharge summary or autopsy reports) to Worldwide Drug Safety via fax or e-mail. If it is not possible to access the EDC system, refer to the procedures outlined above for initial reporting of SAEs.

8.5 Pregnancy Reporting

If the patient or partner of a patient participating in the study becomes pregnant during the study or within 90 days of discontinuing study drug, the Investigator should report the pregnancy to Worldwide Drug Safety within 24 hours of being notified. Worldwide Drug Safety will then forward the Exposure In Utero form to the Investigator for completion.

A patient becoming pregnant while on study drug will immediately be withdrawn from the study and early termination study procedures will be performed.

The patient or partner should be followed by the Investigator until completion of the pregnancy. If the pregnancy ends for any reason before the anticipated date, the Investigator should notify Worldwide Clinical Safety. At the completion of the pregnancy, the Investigator will document the outcome of the pregnancy. If the outcome of the pregnancy meets the criteria for immediate classification as an SAE (ie, postpartum complication, spontaneous abortion, stillbirth, neonatal death, or congenital anomaly), the Investigator should follow the procedures for reporting an SAE.

8.6 Expedited Reporting

The Sponsor will report all relevant information about suspected unexpected serious adverse reactions in accordance with International Council for Harmonisation (ICH) for Good Clinical Practices, Food and Drug Administration (FDA) guidelines, Directive 2001/20/EC of the European Parliament and the CT3 Guideline, and any other local regulations applicable in the participating countries.

The Sponsor or designee will also inform all Investigators as required. When required due to local regulations, the Investigator will provide expedited reports to the Institutional Review Board (IRB)/Independent Ethics Committees (IECs).

8.7 Clinical Laboratory Evaluations

Detailed procedures of sampling preparation, storage, and shipment will be described in a specific laboratory manual, which will be provided to all sites. The visits at which these samples will be collected are shown in the Schedule of Procedures (Appendix A) and the data captured will be forwarded to the central laboratory for evaluation, unless otherwise specified. See Appendix B for a list of clinical laboratory analytes to be measured.

The Investigator should review and evaluate out of range laboratory results. Any clinically relevant abnormal laboratory value should be immediately rechecked whenever possible, for confirmation before making any decision for the concerned patient. It should be documented as an adverse event/SAE as applicable.

8.8 Vital Signs

Vital signs include pulse rate, respiratory rate, and oral temperature. Vital signs will be assessed at the visits indicated on the Schedule of Procedures (Appendix A). Triplicate blood pressure should be taken approximately 2 minutes apart with the patient in the seated position and having rested for at least 10 minutes prior to assessment. Blood pressure and pulse rate will be measured at the same time

8.9 Electrocardiograms

A 12-lead ECG will be performed in triplicate at the visits indicated on the Schedule of Procedures (Appendix A). Patients should be resting in the supine position for at least 10 minutes prior to the assessment. The Investigator will assess ECG data as normal, abnormal not clinically significant, or abnormal clinically significant. Any clinically significant abnormalities should be documented as an adverse event/SAE as applicable. All ECG traces will be kept as source data.

8.10 Physical Examinations

The Investigator or a licensed study team member, per local regulations, will perform physical examinations according to the Schedule of Procedures (Appendix A). Physical examinations will evaluate the following body systems/organs: general appearance; dermatological; head and eyes; ears, nose, mouth, and throat; pulmonary; cardiovascular; abdominal; genitourinary (optional); lymphatic; musculoskeletal/extremities; and neurological. If a system is not assessed, the Investigator or designee will note the reason in the source documents. If a new clinically significant abnormality or worsening from baseline is detected after randomization, then an adverse event should be reported and the patient should be considered for further clinical investigations and/or specialist consultation as per the Investigator's medical judgment.

8.11 Height, Weight, and Body Mass Index

Height will be measured at Screening only. Weight will be measured at the visits indicated in the Schedule of Procedures (Appendix A). Body mass index will be calculated and recorded at Screening and at Day 84.

8.12 Safety Surveillance and Management of Serum Potassium Levels

Serum potassium levels of study patients will be monitored systematically throughout the study. In addition to the clinical laboratory tests pre-defined in the Schedule of Procedures (Appendix A), unscheduled assessments of serum potassium levels are recommended under certain situations (eg, vomiting and/or diarrhea for ≥ 1 day) that may impact patients' serum electrolyte levels or fluid balance.

In patients with serum potassium above the normal laboratory reference range (serum potassium levels $\geq 5.0 \text{ mmol/L}$), it is advised that the Investigator should reinforce dietary restriction for management of elevated potassium and consider local guideline recommendations. Table 1 below summarizes the laboratory testing for assessment of serum potassium levels $\geq 5.0 \text{ mmol/L}$ and guidelines for management of study drug, which includes continuation thereof, holding of study drug, and/or discontinuation of study drug. If serum potassium levels are < 5.0 mmol/L, no action is indicated. A serum potassium level of $\geq 5.6 \text{ mmol/L}$ requires a hold of study drug and appropriate retesting and intervention as described in Table 1. A potassium level of $\geq 6.0 \text{ mmol/L}$ necessitates immediate and permanent discontinuation of study drug.

Because of potential issues anticipated from routine sample handling and extended transportation time to the central laboratory, pseudohyperkalemia secondary to hemolysis may occur in centrally analyzed laboratory samples. For this reason, during treatment with study drug, all serum potassium assessments, including retests, will be performed at both local and central laboratories.

In general, if the initial local and/or central laboratory test shows that a patient's serum potassium level is ≥ 5.3 mmol/L, a repeat local test is required to confirm elevation of serum potassium levels and dictate actions to be taken as outlined in Table 1. All samples should be screened for hemolysis to eliminate the possibility of pseudohyperkalemia. Results from the central laboratory will be used for data analysis. If a major discrepancy exists between the local and central laboratory values, defined as a ± 0.3 mmol/L difference between values or if hemolysis is noted in the specimens, repeat blood samples should be obtained to confirm eligibility or continuation in the study. Again, decisions to enroll or randomize a patient should generally be based on the local serum potassium. However, if the central laboratory serum potassium is ≤ 4.8 mmol/L and the local potassium test is > 4.8 mmol/L, the more conservative value may be used if the difference between the 2 samples is ≤ 0.3 mmol/L. 10

Serum potassium recheck is recommended within 24, 48, or 72 hours, depending on the level of hyperkalemia, following Investigator notification of a serum potassium ≥ 5.3 mmol/L (see Table 1). The Investigator can perform additional serum potassium retests when clinically indicated for medical conditions or procedures that occur during the study. Blood samples should be obtained atraumatically, without fist clenching or prolonged use of a tourniquet. Non-hemolyzed blood samples sent for rechecks or retests will be analyzed in both local and central laboratories. In some circumstances, as outlined below in Table 1, a second retest may be indicated and should be performed within 1 week to allow the patient to adjust to the withdrawal of study drug (if indicated) and application of standard of care. All episodes of hyperkalemia, serum potassium of ≥ 5.0 mmol/L should be reported as an adverse event of special interest.

The monitoring of serum potassium and the decision on whether or not to discontinue study drug, as well as other interventions, are outlined in Table 1.

Table 1. Potassium Safety Monitoring – Reporting / Management of Hyperkalemia

	Alert Local and Central Laboratory Serum Potassium (K+) Values			
	> 5.0 to 5.2 mmol/L	5.3 to 5.5 mmol/L	5.6 to 5.9 mmol/L	≥ 6.0 mmol/L
Following notification of a serum K ⁺ alert value ¹		Contact patient and schedule repeat serum K ⁺ within 24-72 hours after laboratory notification.	Contact patient and schedule repeat serum K ⁺ within 24-48 hours after laboratory notification.	Contact patient and schedule repeat serum K ⁺ within 24 hours after laboratory notification.
Management	Continue study drug.	Continue study drug pending retest results.	Hold study drug pending retest results.	Permanently discontinue study drug.
Treatment If first serum K ⁺ retest is < 5.3 mmol/L	Reinforce low K ⁺ diet.	Reinforce low- K ⁺ diet; manage HK per local SOC (no K ⁺ binders). Continue study drug.	Reinforce low- K ⁺ diet; manage HK per local SOC (no K ⁺ binders). Resume study drug.	Reinforce low- K ⁺ diet; manage HK per local SOC (may use K ⁺ binders)
Management following first serum K ⁺ retest		If retest serum K ⁺ is ≥ 5.3 to 5.5 mmol/L: 1. Hold study drug, 2. Consider higher dose of diuretic, 3. Schedule second serum K ⁺ retest within 1 week. If retest serum K ⁺ > 5.5 mmol/L, permanently discontinue study drug.	 If retest serum K⁺ is ≥ 5.3 to 5.5 mmol/L: 1. Continue to hold study drug, 2. Consider higher dose of diuretic, 3. Schedule second serum K⁺ retest within 1 week. If retest serum K⁺> 5.5 mmol/L, permanently discontinue study drug. 	Note: Following discontinuance of study drug continue study visits and safety monitoring.
Management following second serum K ⁺ retest		If serum K ⁺ on retest is < 5.3 mmol/L, continue study drug. If serum K ⁺ on retest is ≥ 5.3 mmol/L, permanently discontinue study drug.	If serum K ⁺ is < 5.3 mmol/L, resume study drug. If serum K ⁺ on retest is ≥ 5.3 mmol/L, permanently discontinue study drug.	
Adverse Event Reporting		Report as AE of Special Interest	Report as AE of Special Interest	Report as AE as Special Interest

In the absence of hemolysis, the more conservative value from the central or local laboratories should be used to guide management and treatment Study sites should make repeated attempts to contact patients with high K⁺ or HK to ensure compliance with K⁺ safety monitoring and required retests.

If the serum K^+ levels are ≥ 5.3 mmol/L, repeat local and central serum K^+ testing is required in compliance with the above management strategies and procedures. The Investigator should consider local guideline and SOC for management of serum potassium levels above the normal laboratory reference range. In all instances, dietary restriction for management of elevated potassium should be reinforced. Consider use of higher dose of loop or thiazide like diuretics to manage HK. If chronic or intermittent treatment with potassium-binders is required, the patient should be permanently discontinued from study drug.

If the locally analyzed blood sample is missing, or the result is inconclusive, another blood sample should be taken as soon as possible but no later than 24 to up to 72 hours to confirm the value.

The Sponsor or delegate will be notified by site personnel within 24 hours of the site being aware of results for any local laboratory potassium value ($\geq 5.3 \text{ mmol/L}$). Retest/confirmatory testing results will be forwarded to the Sponsor or delegate within 24 hours of the site being aware of results.

Abbreviations: K⁺: potassium, HK: hyperkalemia, SOC: Standard of care.

Regardless of whether a patient will discontinue study drug due to elevated serum potassium levels, he/she should be closely monitored and treated, as appropriate, per the Investigator's assessment.

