8 SAFETY ASSESSMENTS

Safety variables will include adverse events, vital signs (pulse rate, respiratory rate, and oral temperature), clinical laboratory findings, 12-lead ECGs, and physical examination findings.

The following serum potassium/hyperkalemia-related parameters and renal function-related parameters will be collected and evaluated:

- Incidence of hyperkalemia (defined as serum potassium ≥ 5.6 mmol/L), incidence of severe hyperkalemia (defined as serum potassium ≥ 6.0 mmol/L), and incidence of patients with serum potassium > 5.0 mmol/L;
- Change in serum potassium level from baseline to Day 84; and
- Change in eGFR and creatinine levels > 30% throughout the study period.

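### The hyperkalemia incidence counts rest on central results, with no rule to drop hemolyzed samples, and can omit local-only elevations that led to a hold or stop

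*Combined protocol and SAP*

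**What the plan says.** **Analysis.** Section 8.12: "Results from the central laboratory will be used for data analysis". Section 8 and the secondary objectives (Section 2.2) list incidence at > 5.0, ≥ 5.6 and ≥ 6.0 mmol/L. They name no laboratory, so the Section 8.12 sentence governs.

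**Reliability of the central value.** Section 8.12 says that "pseudohyperkalemia secondary to hemolysis may occur in centrally analyzed laboratory samples", and gives this as the reason why, on treatment, "all serum potassium assessments, including retests, will be performed at both local and central laboratories". It adds: "All samples should be screened for hemolysis to eliminate the possibility of pseudohyperkalemia". Repeat samples are called for when hemolysis is noted or the two laboratories differ by 0.3 mmol/L. The stated purpose is eligibility or continuation, not analysis.

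**Action on study drug.** The note to Table 1 reads: "In the absence of hemolysis, the more conservative value from the central or local laboratories should be used to guide management and treatment". The text before the table says that at 5.3 mmol/L or above "a repeat local test is required to confirm elevation of serum potassium levels and dictate actions to be taken as outlined in Table 1". The text after the table requires repeat testing at both laboratories. At 5.3 to 5.9 mmol/L a permanent stop needs a retest; at ≥ 6.0 mmol/L it is immediate.

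**Event reporting.** Section 8.2 defines mild and moderate hyperkalemia of special interest from either laboratory, and names no laboratory for severe events. Section 9.2.3 bases safety on adverse events as well as laboratory abnormalities.

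**The concern.** The plan doubts one source of potassium values, adds a second source because of that doubt, and then analyzes the first. Hemolyzed values are set aside when treatment is decided, but nothing sets them aside when incidence is counted. A sound local value that leads to a hold or stop, on the other hand, has no place in a central-only count.

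Hyperkalemia is a listed secondary objective and a main risk the protocol discusses for this drug class. With 80 patients per group, a few misclassified patients can change how the doses compare with placebo. Readers will also set the incidence table beside the holds, stops and adverse events, and the plan gives them no way to reconcile these.

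**Working it through.** The plan gives no hyperkalemia rate, hemolysis rate or local-central agreement, so there is no figure to reproduce. The check is a comparison of the rules, followed by two illustrations on assumed inputs.

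**1. The rules side by side, for one visit**

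| Result pair | Treatment rule (Table 1 note) | Incidence count | Special-interest event |
|---|---|---|---|
| Both high, no hemolysis | Acted on | Counted | Reported |
| Central high and hemolyzed, local normal | Central value set aside | Counted; no exclusion stated | Section 8.1 does not require reporting of a test judged an error |
| Local high without hemolysis, central below threshold | Acted on | Not counted, unless another central sample reaches the threshold | Reported (mild and moderate); laboratory unstated for severe |

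The second row adds to the incidence and the third takes away from it. The net sign is therefore open.

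**2. Effect of false central elevations on the comparison**

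Inputs, all assumed: true patient-level rates p of 2% and 6%; the same per-patient false-positive rate f in both arms, independent of the true event. Observed rate = p + (1 − p) × f. With no false positives the ratio is 6/2 = 3.0 and the difference is 4.0 points.

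- f = 1%: 0.02 + 0.98 × 0.01 = 2.98%; 0.06 + 0.94 × 0.01 = 6.94%. Ratio 2.3, difference 3.96 points.
- f = 3%: 0.02 + 0.98 × 0.03 = 4.94%; 0.06 + 0.94 × 0.03 = 8.82%. Ratio 1.8, difference 3.88 points.
- f = 5%: 0.02 + 0.98 × 0.05 = 6.90%; 0.06 + 0.94 × 0.05 = 10.70%. Ratio 1.6, difference 3.80 points.

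The ratio is pulled toward 1; the difference barely moves.

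**3. Both errors together, at ≥ 5.6 mmol/L**

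Simulation of 400,000 patients. Assumed inputs: patient mean potassium 4.7 (SD 0.35), visit-to-visit SD 0.25, error SD 0.10 to 0.20 in each laboratory, 0% to 5% of central samples hemolyzed with 0.5 mmol/L added, no local hemolysis, values rounded to 0.1. There are six on-treatment visits (Days 7, 14, 28, 42, 56 and 84 in Appendix A). Retests and drug holds are ignored. The comparator is any non-hemolyzed value from either laboratory at or above the threshold. Entries are percentages of patients.

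| Error SD | Hemolysis | Central-only | Either laboratory, non-hemolyzed | In second, not first | In first, not second |
|---|---|---|---|---|---|
| 0.10 | 0% | 9.6 | 11.8 | 2.2 | 0.0 |
| 0.10 | 5% | 13.6 | 11.8 | 1.9 | 3.7 |
| 0.15 | 0% | 11.3 | 14.8 | 3.5 | 0.0 |
| 0.15 | 5% | 15.4 | 14.6 | 2.9 | 3.6 |
| 0.20 | 0% | 13.8 | 18.6 | 4.9 | 0.0 |
| 0.20 | 5% | 17.7 | 18.4 | 4.2 | 3.4 |

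Central-only incidence falls below or above the comparator depending on the inputs. The mismatch is 1.9% to 4.9% of patients one way and 0% to 3.7% the other. Per group of 80 that is 0.019 × 80 = 1.5 to 0.049 × 80 = 3.9 patients, and 0 to 0.037 × 80 = 3.0 patients. The rate on error-free values was 8.3% to 8.4%, below both counts, so the either-laboratory figure is a second view and not the truth.

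**The case against.** The case on the other side is substantial, and most of it limits the point.

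- *Safeguards exist.* All samples are to be screened, hemolysis or a 0.3 mmol/L discrepancy triggers repeat samples, and retests go to both laboratories, so an elevation first seen locally may still reach the central data. This stands and makes the mismatch smaller. It does not say what happens to a flagged value in the count.
- *Local events are not lost.* Special-interest reporting takes central or local values for mild and moderate events, and adverse events are analyzed. This stands. The gap is confined to the laboratory-threshold counts.
- *The endpoint is not a count of actions.* A second retest at 5.3 mmol/L or above can end treatment, while the hyperkalemia endpoint starts at 5.6. The two would differ even with one laboratory. This stands, so exact agreement is not the aim.
- *One central laboratory across about 90 sites is a reasonable way to harmonize.* Agreed, and the main count should stay central.

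A reader might infer that drug is stopped on whichever laboratory is higher. The documents do not support that: the Table 1 note applies only without hemolysis, and at 5.3 to 5.9 mmol/L a permanent stop needs a retest. A reader might also infer that the endpoint is biased in a known direction. The two errors oppose each other and no rate is given, so the direction is not determined.

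**Conclusion.** The point holds in limited form. As written, the three threshold counts use central values, including any that are hemolyzed, and can omit a sound local-only elevation that led to a hold or stop. They can therefore differ from the events acted on, in either direction.

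The size is not derivable from the documents. On assumed inputs, false positives in 1% to 5% of patients would lower a true ratio of 3.0 to between 2.3 and 1.6, with the difference still near 4 points. The simulated mismatch is at most about four patients per group one way and three the other, before allowing for retests. The 1% to 5% range and the simulation inputs are illustrative.

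The primary endpoint and the sample size are unaffected. This is still more than missing detail, because the stated rule, followed literally, counts values that the protocol itself distrusts.

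**What to change.** 1. Keep central values for mean change in potassium and for the main incidence counts.
2. Exclude samples flagged as hemolyzed from the > 5.0, ≥ 5.6 and ≥ 6.0 mmol/L counts, and state whether unscheduled central samples enter them.
3. Pre-specify one sensitivity count by arm at the same thresholds, using any non-hemolyzed value from either laboratory, scheduled or unscheduled.
4. Do not require confirmation on retest. At 5.6 to 5.9 mmol/L drug is held before the retest, so a genuine on-drug elevation could fall and be removed. At > 5.0 to 5.2 mmol/L Table 1 calls for no retest.
5. Reconcile the three statements in Section 8.12 on which test drives action: the text before Table 1, the table note and the text after it. No clinical rule is proposed here.

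Cost: analysis wording and one more table. Local values and hemolysis flags must be in the analysis database; the documents require the tests and the screening but do not say that the flags are captured. Two incidence figures will need explaining, and the sensitivity figure will tend to run high because it takes the larger of two measurements.
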